Quality Assurance
Quality Control
Randomised Controlled Trial
Research Ethics Committee
Serious Adverse Event
Source Document Verification
Standard Operating Procedure
Site Specific Assessment
Trial Management Group
Trial Steering Committee

3. SUMMARY/SYNOPSIS

Short Title	MODET			
Method	Multi-site prospective observational study			
Research Sites	Major Trauma Centres (MTC) within the Pan-London Major Trauma System: Royal London Hospital, Barts Health NHS Trust St Marys Hospital, Imperial College Healthcare NHS Trust Kings College Hospital, King's College Hospital NHS Foundation Trust St Georges Hospital, St George's University Hospitals NHS Foundation Trust			
Objectives/Aims	This study aims to: Identify the prevalence, severity and patterns of multiple organ dysfunction syndrome (MODS) Determine predictors and risk factors of developing MODS Identify age related characteristics that contribute to MODS Examine the mode of mortality associated with MODS Analyse the relationship between MODS and longer-term recovery and quality of life			
Number of	1346			
Participants/Patients				
Main Inclusion Criteria	Inclusion criteria: Adult patients (≥16 years of age) with multiple injuries admitted to adult critical care unit within the four London MTCs.			
Statistical Methods and Analysis	 Analysis populations: Patients who are greater than 64 years of age will comprise the older-age cohort and younger patients (controls) are defined as ≤64 years. Primary outcome analysis: Difference in proportion will be examined with chi squared or fishers exact tests. Secondary outcome analysis: Univariate analysis of variables between the two age groups will be conducted using unpaired students t-tests or Mann Whitney U tests. Analysis of more than two groups or variables will be conducted using ANOVA or Kruskal Wallis tests. 			
Proposed Start Date	1 st February 2017			
Proposed End Date	1 st May 2020			
Study Duration	Three years			

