Previously, we have examined the relationship between trauma and adverse outcomes but have not specifically focused on older patients ²⁰⁻²². It is possible that the immune systems of older patients react differently to injury when compared to younger cohorts, and this may increase vulnerability to MODS ^{14,23,24}. Decreased skeletal muscle mass in older people is reported to impair immune system function in intensive care patients²⁵ and severe injury may further alter immune cell activity, causing physiological changes leading to adverse outcomes^{26,27}. Altered metabolism after trauma is associated with increased inflammatory responses²⁸ and together with the nutritional deficits observed in critically injured older people²⁹ these may contribute to age-related MODS. Frailty is also known to reduce physiological function ^{30,31} and frailty in older people independently predicts in-hospital complications such as pneumonia or deep vein thrombosis after injury ³². Therefore it may be that frailty rather than age increases the risk of MODS after severe injury. Previous trauma studies suggest that both older age and frailty are associated with decreased longer-term independence after injury ^{32,33}. However the impact of MODS on longer-term function, dependence and recovery in older people has not been investigated. The lack of UK-based evidence means that the prevalence, predictors and outcomes of MODS in our older trauma patients are unknown.

This prospective observational study will evaluate the patterns of MODS in trauma patients and determine to what extent it is related to ageing and frailty. By understanding specific age-related predictors or drivers of MODS we aim to identify treatment or prevention strategies which will enhance recovery for severely injured older people. MODS is also associated with late, indolent death, and by studying patterns of this mortality in older patients we may be able to prognosticate futility. This may enable stratification of older patients most likely to respond to intervention and those who would benefit from supportive or palliative care. Finally, evidence of how MODS impacts longer-term recovery and quality of life will support rehabilitation practice, and where appropriate, self-managed recovery for older trauma patients and their support networks.

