6. METHODOLOGY

Study Design

This is a pan-London prospective observational study which aims to characterise organ dysfunction in older trauma patients \geq 65 years. All adults admitted to an adult critical care unit within one the London Major Trauma Centres (MTCs) will be considered for enrolment, with younger patients (<65 years) recruited as a control group.

Settings

There are four MTCs in London. Each site will have a nominated Principal Investigator (PI). Organ injury scoring training will be provided for local research nurses or data collectors prior to study commencement. Two funded research nurses from Queen Mary University of London (QMUL) will support patient enrolment, data collection and data quality monitoring across the four MTCs. Each site will be supported by an on-line information folder with the protocol, guidance/explanatory notes and contact details of the Principal Investigator. For this study, a critical care unit is defined as either an Intensive Care Unit (Level 3 care) or a combined unit of Intensive Care (Level 3 care) and High Dependency Unit (Level 2 care).

Inclusion Criteria

- Adult major trauma patients (≥16 years of age) admitted to adult critical care within one of the four London Trauma System MTCs. This includes direct admissions from the Emergency Department, admissions from the operating theatre or from a ward, transfers from other facilities and readmission to critical care.

Exclusion Criteria

- Patients with a burns-only injury
- Patients who are prisoners
- Patients who decline to provide informed consent or do not have consultee consent

Study Design / Plan – Study Visits

Trauma patients (≥16 years of age) admitted to MTC critical care during the enrolment phase of the study (two years in total) will be identified by the local PI together with clinical care staff. The local PI will be responsible for ensuring patient enrolment, participant consent, data collection, patient detail de-identification, data entry and storage. Data from routine clinical care records will be recorded daily by local and QMUL research nurses whilst the patient is admitted to the critical care unit.

The clinical data collection will include:

- Demographics: Age within a range, gender, co-morbid disease, pre-injury medication
- Injury variables: Mechanism of injury, Injury Severity Score (ISS)
- Organ dysfunction: The frequency, pattern and severity will be measured daily using Sequential Organ Failure Assessment (SOFA) scoring

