Univariate analysis of variables between the two age groups (< 65 years and ≥65 years) will be conducted using unpaired students t-tests or Mann Whitney U tests (for parametric and non-parametric data respectively). Analysis of more than two groups (for example thresholds of immune counts or degrees of organ dysfunction) will be conducted using ANOVA or Kruskal Wallis tests. Chi-squared statistic or Fisher's exact tests will be used to compare proportions of MODS between the two cohorts.

Multivariable regression analysis will be used to determine statistically independent relationships between MODS and age plus other significant independent variables (such as the effect of injury severity, blood transfusion, on the development of MODS). Multivariate linear regression will be used to analyse continuous dependent variables and binary logistic regression for binary dependent variables. Results of linear regression will be reported as Beta co-efficient with 95% confidence intervals, and for logistic regression adjusted Odds ratios (OR) with 95% confidence intervals.

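### The synopsis gives primary status only to a crude age comparison of MODS and omits the planned adjusted model, which is what the ageing aim needs

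*Protocol*

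**What the plan says.** Protocol section 3 (Summary/Synopsis, Statistical Methods and Analysis) gives one analysis for the primary outcome: "Difference in proportion will be examined with chi squared or fishers exact tests". The entry for secondary outcomes lists univariate tests. No regression appears anywhere in the synopsis.

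Section 6 (Methods of analysis) repeats the crude test: "Chi-squared statistic or Fisher's exact tests will be used to compare proportions of MODS between the two cohorts". It then goes further: "Multivariable regression analysis will be used to determine statistically independent relationships between MODS and age plus other significant independent variables". The covariates are illustrated by a parenthesis, "such as the effect of injury severity, blood transfusion, on the development of MODS", and the results are to be given as "for logistic regression adjusted Odds ratios (OR) with 95% confidence intervals". The text does not rank the crude test and the model against each other.

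The Introduction (section 4) says the study will evaluate patterns of MODS and "determine to what extent it is related to ageing and frailty". Section 5 lists prevalence as one objective, and predictors and age-related characteristics as others. The data list in section 6 includes mechanism of injury, ISS, co-morbid disease and the Edmonton Frail Scale. The study is observational, and patients under 65 serve as the control group.

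**The concern.** Two questions share one contrast. The first is how common MODS is in older and in younger critical care trauma patients. A crude difference in proportions answers that. The second is how far age itself, at a given injury, is related to MODS. A crude difference does not answer that, because age groups are not randomised and may arrive with different injuries. The protocol itself treats injury severity as a determinant of MODS, since it names it for the regression.

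A reader of the synopsis finds only the crude test and a group called controls, and will tend to read the result as an age effect. The model that could carry that reading has no stated standing. The wording about significant variables also leaves open that ISS could be dropped if its p value is unremarkable, or that transfusion, which follows injury, could enter beside it. What is at stake is which age effect is reported as the answer to the ageing aim, and whether it can be chosen after the data are seen.

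**Working it through.** **1. The sample size belongs to the crude contrast.** Inputs from section 6: 0.33 older, 0.23 younger, alpha 0.05, power 0.80, and allocation k = 414/259 = 1.598. Two-sided testing is assumed, because the text does not say.

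- Pooled proportion = (0.33 + 1.598 × 0.23)/2.598 = 0.2685.
- n older = [1.960·√(0.2685 × 0.7315 × (1 + 1/k)) + 0.842·√(0.33 × 0.67 + 0.23 × 0.77/k)]² / 0.10² = (1.107 + 0.485)²/0.01 ≈ 254, with 254 × 1.598 ≈ 406 younger.
- The protocol states 259 and 414, which is about 2% higher. Power at 259 v 414 is 0.81, and at the full 518 v 828 it is 0.98.

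So the plan's figure reproduces for an unadjusted comparison of two proportions.

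**2. What injury mix can do to the crude difference.** If the age effect is the same among severely and less severely injured patients, then

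crude difference = age effect within strata + (share severe in older − share severe in younger) × (MODS risk if severe − MODS risk if not).

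The documents give neither factor of the last term, so both are assumed. With a within-stratum age effect of 10 points, the crude difference in points is:

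| Older minus younger, share severe | Severity adds 20 points | 30 points | 40 points |
|---|---|---|---|
| −20 points | 6 | 4 | 2 |
| −10 points | 8 | 7 | 6 |
| +10 points | 12 | 13 | 14 |
| +20 points | 14 | 16 | 18 |

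With the younger rate held at 23%, the chance of a significant crude test at 518 v 828 is 0.13, 0.38, 0.69, 0.90 and 0.98 for crude differences of 2, 4, 6, 8 and 10 points, and above 0.99 from 12 points upward.

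The same figures cover the opposite error. With no age effect within strata and older patients more often severely injured by 10 to 20 points, the crude difference is 2 to 8 points. The chance of a significant result that reflects injury mix alone is then 0.13 to 0.90.

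**3. What adjustment costs.** Approximation: required n = 673/(1 − R²), where R² is the share of variance in age group explained by the covariates. R² is assumed, and the age effect is taken to be as large as the planned contrast.

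| R² | n for power near 0.80 | Power at 1346 |
|---|---|---|
| 0 | 673 | 0.98 |
| 0.1 | 748 | 0.97 |
| 0.2 | 841 | 0.95 |
| 0.3 | 961 | 0.92 |
| 0.5 | 1346 | 0.81 |

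Expected MODS cases: 518 × 0.33 + 828 × 0.23 = 170.9 + 190.4 ≈ 361, enough for a model with a few forced covariates.

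**The case against.** The strongest reply is that nothing is missing. The crude test matches the prevalence objective and tests exactly the null hypothesis in the sample-size text. As a description of prevalence it is not confounded. The adjusted model is already planned, names injury severity and promises confidence intervals. The synopsis label may simply sort analyses by outcome, so that the logistic model of MODS is also an analysis of the primary outcome. Covariate detail is commonly left to the SAP, which is not shown.

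Most of this stands. The crude test should stay, and a bare absence of covariate detail would be no finding. What remains is that the protocol has itself chosen what the synopsis presents for the primary outcome, has left the model out there, and has described the covariates by significance. A SAP could fill in detail, but the synopsis wording would still need to change.

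A reader might infer two stronger claims, and the documents support neither. One is that the age comparison is confounded by case mix. There are no injury data by age group, so whether there is bias, in which direction and how large are all unknown. The other is that the study will lose power. The 0.98 applies to a crude 33% v 23%. If those crude rates hold, power is unchanged whatever the injury mix, and a mix in the other direction raises the crude difference.

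Nor does it follow that every collected covariate should be forced in. Co-morbidity and frailty may lie on the path from age to MODS, and adjusting for them could understate the overall age effect.

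**Conclusion.** The point holds as an inexpensive improvement, not as a demonstrated bias. The crude test is right for prevalence but cannot carry the ageing aim, and the protocol does not say which age effect does. Under the assumed ranges in the working, injury mix could move the crude difference by 2 to 8 points in either direction, so a 10-point age effect could appear as anything from 2 to 18 points. These are illustrations of scale, not estimates for this population. The planned sample supports an adjusted main analysis: approximate power is 0.92 to 0.97 for assumed R² of 0.3 to 0.1, and 0.81 at 0.5.

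**What to change.** - **Prevalence:** keep the crude difference in MODS between age groups, with its 95% confidence interval, as the answer to the prevalence objective.
- **Age effect:** name the logistic model of MODS on age group as the main analysis, with ISS, mechanism and centre forced in whatever their significance. Add it to the synopsis, and replace the wording about significant variables in section 6.
- **Second model:** add co-morbidity and frailty, and say that it asks how much of the age effect runs through them.
- **Post-injury variables:** keep variables such as transfusion out of the main model.
- **Reporting:** show crude and adjusted effects side by side on the same scale. Odds ratios can change on adjustment even without confounding, so a standardised risk difference beside the adjusted odds ratio would help.
- **Sample-size text:** state that the size was based on the crude contrast, and give the approximate power of the adjusted comparison with its assumed R².

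The cost is wording in the synopsis and section 6, plus somewhat less power than the crude test. The model is already planned, ISS, mechanism, co-morbidity and frailty are already collected, centre is known by design, and no extra patients are needed.

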4. INTRODUCTION

For the first time there are 11 million people aged 65 or over in the UK¹. The number of older people suffering traumatic injury is increasing ²⁻⁶. In those who survive the initial period after injury a significant proportion goes onto develop adverse events such as multiple organ dysfunction (MODS) ^{7,8}. This occurs as a result of an exaggerated systemic inflammatory response following major tissue trauma⁹, where one or more organs do not function as they did prior to the traumatic injury. Recent reports suggest that MODS affects up to 33% of trauma patients ^{7,10-12}. Younger injured people who develop MODS usually recover quickly¹³, whereas older patients appear to suffer prolonged organ dysfunction, which is complicated by persistent immunosuppression and infectious episodes^{10,14,15}. This extends hospital stay, increases resource use and delays recovery after trauma ^{11,12}. MODS in older people is also associated with increased mortality ¹⁶⁻¹⁸ characterised by late, indolent death ^{14,19}. International evidence suggests that older age is strongly associated with MODS after trauma ^{7,11,12,14}, however the age-related characteristics that contribute to this burden in the UK have not been reported.

Previously, we have examined the relationship between trauma and adverse outcomes but have not specifically focused on older patients ²⁰⁻²². It is possible that the immune systems of older patients react differently to injury when compared to younger cohorts, and this may increase vulnerability to MODS ^{14,23,24}. Decreased skeletal muscle mass in older people is reported to impair immune system function in intensive care patients²⁵ and severe injury may further alter immune cell activity, causing physiological changes leading to adverse outcomes^{26,27}. Altered metabolism after trauma is associated with increased inflammatory responses²⁸ and together with the nutritional deficits observed in critically injured older people²⁹ these may contribute to age-related MODS. Frailty is also known to reduce physiological function ^{30,31} and frailty in older people independently predicts in-hospital complications such as pneumonia or deep vein thrombosis after injury ³². Therefore it may be that frailty rather than age increases the risk of MODS after severe injury. Previous trauma studies suggest that both older age and frailty are associated with decreased longer-term independence after injury ^{32,33}. However the impact of MODS on longer-term function, dependence and recovery in older people has not been investigated. The lack of UK-based evidence means that the prevalence, predictors and outcomes of MODS in our older trauma patients are unknown.

This prospective observational study will evaluate the patterns of MODS in trauma patients and determine to what extent it is related to ageing and frailty. By understanding specific age-related predictors or drivers of MODS we aim to identify treatment or prevention strategies which will enhance recovery for severely injured older people. MODS is also associated with late, indolent death, and by studying patterns of this mortality in older patients we may be able to prognosticate futility. This may enable stratification of older patients most likely to respond to intervention and those who would benefit from supportive or palliative care. Finally, evidence of how MODS impacts longer-term recovery and quality of life will support rehabilitation practice, and where appropriate, self-managed recovery for older trauma patients and their support networks.

5. STUDY OBJECTIVES

This study aims to:

- Identify the prevalence, severity and patterns of MODS in older patients
- Determine predictors and risk factors of developing MODS for older patients
- Identify age related characteristics that contribute to MODS
- Examine the mode of mortality associated with MODS
- Analyse the relationship between MODS and longer-term recovery and quality of life for older patients

The primary outcome is the presence of MODS during the critical care admission period. An individual Sequential Organ Failure Assessment (SOFA) score of 1 in any organ represents dysfunction. Multiple organ dysfunction syndrome (MODS) is defined as a total daily SOFA score of >5.

Secondary outcomes are in-hospital mortality, ventilator use, level of organ support, adverse events such as infection or stroke, critical care stay and total length of stay. Longer terms outcomes are quality of life and recovery at one year post injury.

6. METHODOLOGY

Study Design

This is a pan-London prospective observational study which aims to characterise organ dysfunction in older trauma patients \geq 65 years. All adults admitted to an adult critical care unit within one the London Major Trauma Centres (MTCs) will be considered for enrolment, with younger patients (<65 years) recruited as a control group.

Settings

There are four MTCs in London. Each site will have a nominated Principal Investigator (PI). Organ injury scoring training will be provided for local research nurses or data collectors prior to study commencement. Two funded research nurses from Queen Mary University of London (QMUL) will support patient enrolment, data collection and data quality monitoring across the four MTCs. Each site will be supported by an on-line information folder with the protocol, guidance/explanatory notes and contact details of the Principal Investigator. For this study, a critical care unit is defined as either an Intensive Care Unit (Level 3 care) or a combined unit of Intensive Care (Level 3 care) and High Dependency Unit (Level 2 care).

Inclusion Criteria

- Adult major trauma patients (≥16 years of age) admitted to adult critical care within one of the four London Trauma System MTCs. This includes direct admissions from the Emergency Department, admissions from the operating theatre or from a ward, transfers from other facilities and readmission to critical care.

Exclusion Criteria

- Patients with a burns-only injury
- Patients who are prisoners
- Patients who decline to provide informed consent or do not have consultee consent

Study Design / Plan – Study Visits

Trauma patients (≥16 years of age) admitted to MTC critical care during the enrolment phase of the study (two years in total) will be identified by the local PI together with clinical care staff. The local PI will be responsible for ensuring patient enrolment, participant consent, data collection, patient detail de-identification, data entry and storage. Data from routine clinical care records will be recorded daily by local and QMUL research nurses whilst the patient is admitted to the critical care unit.

The clinical data collection will include:

- Demographics: Age within a range, gender, co-morbid disease, pre-injury medication
- Injury variables: Mechanism of injury, Injury Severity Score (ISS)
- Organ dysfunction: The frequency, pattern and severity will be measured daily using Sequential Organ Failure Assessment (SOFA) scoring
- Total number of days on organ support (CTCOFR score)
- Immune cell function: Daily clinical measures of lymphocyte and neutrophil counts
- Adverse events: Such as infection, delirium, stroke or cardiac dysfunction
- Nutrition: Nutritional requirements, nutrition intake and weight measurements
- Frailty screening using the Edmonton Frail Scale (https://www.nscphealth.co.uk/edmontonscale-pdf)
- Length of stay: In critical care and total hospital stay
- Mortality: Mode and timing

[figure not shown]
As soon as clinically appropriate (determined by the clinical care team in charge of the patient), consent will be sought for inclusion of data into the study and long term follow up. If the patient remains incapacitated due to injury or treatment, consent will be sought from a personal or nominated consultee.

At 12 months post injury patients will be approached by letter, email or telephone (according to patient wishes) and health-related quality of life and longer-term recovery data will be collected using the EuroQol-5D (EQ5D) questionnaire. This was chosen as it has been previously validated to capture outcomes in trauma patients including older people and takes approximately 15 minutes to complete.

Study Scheme Diagram

Each MTC will be identified by a number rather than name.

Eligible trauma patients admitted to the critical care unit during the study period will be identified by the clinical care team.

The PI and research nurses have responsibility to ensure patient anonymity is protected and maintained. They will also ensure that patient identities are protected from any unauthorised parties. Information regarding study patients will be kept confidential and managed in accordance with the Data Protection Act, NHS Caldicott Guardian, The Research Governance Framework for Health and Social Care and Research Ethics Committee Approval.

Although patient identifiable data will be available to research staff they will not be entering it on to the paper case record form (CRF). The de-identified data required for this study is already recorded as part of routine clinical care and as part of the Intensive Care National Audit and Research Centre (ICNARC) audit. Organ failure scoring is not usually conducted as part of routine clinical care however it uses parameters that are recorded by critical care clinical staff on a daily basis.

Paper CRFs will be stored within a locked office in each centre (only accessible to the centre PI and data collectors) and then entered onto the password protected study website by QMUL research nurses.

A password protected coding log which will include identifiable patient data (name, address and date of birth) for patients who have consented to long term outcome follow-up. This will be transferred to [name] (CI) at the end of the in-hospital data collection period. At ten months after injury the NHS Health and Social Care Information Centre (NHS Spine) or patients General Practitioner (GP) will be contacted to ensure that the patient is still alive at this time point. This will avoid erroneous long term follow up and exposing relatives to undue distress. At 12 months post injury, the EQ5D and questionnaire will be administered to each participant who has provided informed consent.

	In critical care	At discharge from hospital	10 month post injury NHS spine check/GP check	12 months post injury
Enrolment	х			
CRF initiation	х			
Informed	х			
consent				
Daily SOFA score	х			
and outcomes				
recorded				
CRF completion		х		
Long term			х	х
follow up				

Schedule of Assessment

End of Study Definition

The study will be formally completed when 12 month follow up for all patients has been obtained and data analysis is complete.

Sample size:

We are planning a study of older patients (≥65 years) and younger (<65 years) controls. Prior research data suggest that the MODS rate among younger patients is 23% and for older patients is 33%. If the true MODS rate in older people is 0.33, we will need to include 259 older subjects and 414 younger subjects per year to be able to reject the null hypothesis that the prevalence of MODS for older and younger patients is equal (power 0.80, alpha 0.05). The total sample size for the two year period is 1346 (518 older patients and 828 younger controls). Each London MTC will aim to enroll:

130 older patients (>64 years) and 207 younger patients (<65 years).

Methods of analysis:

Statistical analysis will be performed using SPSS v.23 (IBM Corporation, Armonk, NY,USA). A p value of <0.05 is considered statistically significant for univariate analysis. De-identified data will be cleaned and categorical data formatted into binary fields for analysis. Normal distribution will be assessed with the Shapiro-Wilk test.

Univariate analysis of variables between the two age groups (< 65 years and ≥65 years) will be conducted using unpaired students t-tests or Mann Whitney U tests (for parametric and non-parametric data respectively). Analysis of more than two groups (for example thresholds of immune counts or degrees of organ dysfunction) will be conducted using ANOVA or Kruskal Wallis tests. Chi-squared statistic or Fisher's exact tests will be used to compare proportions of MODS between the two cohorts.

Multivariable regression analysis will be used to determine statistically independent relationships between MODS and age plus other significant independent variables (such as the effect of injury severity, blood transfusion, on the development of MODS). Multivariate linear regression will be used to analyse continuous dependent variables and binary logistic regression for binary dependent variables. Results of linear regression will be reported as Beta co-efficient with 95% confidence intervals, and for logistic regression adjusted Odds ratios (OR) with 95% confidence intervals.

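### No adverse-event window is stated: as written, outcome recording is tied to the critical care stay, so infection and stroke may be observed for unequal periods in the groups compared

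*Protocol*

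**What the plan says.** Protocol section 5 (Study Objectives) lists among the secondary outcomes "adverse events such as infection or stroke, critical care stay and total length of stay". No time window is attached to the adverse events.

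Protocol section 6, under Study Visits, says that routine clinical data are "recorded daily by local and QMUL research nurses whilst the patient is admitted to the critical care unit". The list of clinical data that follows includes "Adverse events: Such as infection, delirium, stroke or cardiac dysfunction", again without a window. The same list includes "Length of stay: In critical care and total hospital stay" and the mode and timing of death, which for many patients can only be known after critical care.

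The Schedule of Assessment in section 6 marks the row for daily SOFA scoring and outcomes in the critical care column only. In the hospital-discharge column the single mark is for "CRF completion". The text just above the schedule refers to a period of data collection in hospital, without saying what is collected after step-down.

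Under Settings, "a critical care unit is defined as either an Intensive Care Unit (Level 3 care) or a combined unit" with Level 2 beds. A stand-alone Level 2 unit is not named.

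Under Methods of analysis, variables are compared univariately between patients under 65 and those 65 or over.

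**The concern.** The two places that say when outcomes are recorded both point to critical care, and nothing provides for recording an infection or stroke that begins on the ward. A site following the text could record a patient who steps down on day 4 and develops pneumonia on day 9 as event-free. Another site could enter the same event when it completes the form at discharge.

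This matters for the study's rationale. The Introduction says that "older patients appear to suffer prolonged organ dysfunction, which is complicated by persistent immunosuppression and infectious episodes", and that "frailty in older people independently predicts in-hospital complications such as pneumonia or deep vein thrombosis after injury". Such events can fall after step-down. If they are not collected, late complications are under-counted, and a group that stays longer in critical care shows more events simply because it is observed for longer. A SAP can choose an analysis, but it cannot recover events that were never collected, so the collection window has to be settled in the protocol.

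**Working it through.** **Step 1: the text side by side.**

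| Place in the protocol | Points to critical care only | Points to the whole hospital stay |
|---|---|---|
| Section 6, Study Visits | Daily recording during the critical care stay | – |
| Section 6, clinical data list | – | Total hospital stay; mode and timing of death |
| Section 6, Schedule of Assessment | Outcome row marked for critical care only | Form completed at hospital discharge |
| Section 6, text above the schedule | – | Refers to data collection in hospital |
| Section 5, secondary outcomes | – | In-hospital mortality and total stay; adverse events carry no such label |

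No sentence limits adverse events to critical care, and none extends them to the ward. The window is therefore not fixed, and the narrow reading is the one that the explicit recording instructions support.

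**Step 2: what the protocol allows to be calculated.** It gives no adverse-event rate and no length of stay in days. There is no figure of its own to reproduce here, and the size of any distortion cannot be derived. What follows is illustration only.

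**Step 3: illustration under the narrow reading.** Assumptions: the same constant daily risk h in both groups, events counted only in critical care, no deaths and no readmissions.

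Recorded proportion = 1 − (1 − h)^days. For assumed stays of 5 v 12 days:

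- h = 0.03: 1 − 0.97^5 = 14.1%; 1 − 0.97^12 = 30.6%.
- h = 0.02: 1 − 0.98^5 = 9.6%; 1 − 0.98^12 = 21.5%.

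Smaller and other contrasts use the continuous form 1 − exp(−h × days), with the planned 518 older patients given the longer stay and the 828 younger patients the shorter:

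| Assumed stay, older v younger | Daily hazard | Recorded proportions | Apparent risk ratio | Chance of a significant result |
|---|---|---|---|---|
| 7 v 5 days | 0.01 | 6.8% v 4.9% | 1.39 | 0.32 |
| 7 v 5 days | 0.05 | 29.5% v 22.1% | 1.34 | 0.86 |
| 10 v 5 days | 0.01 | 9.5% v 4.9% | 1.95 | 0.90 |
| 10 v 5 days | 0.05 | 39.3% v 22.1% | 1.78 | about 1.00 |
| Equal stays | any | equal | 1.00 | no effect of the window |

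The true risk ratio per day is 1 in every row.

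**Step 4: does a per-day comparison remove it?** Expected days at risk up to a first event = (1 − (1 − h)^days)/h. At h = 0.03 this is 0.1413/0.03 = 4.71 days for a 5-day stay and 0.3062/0.03 = 10.21 days for a 12-day stay. Events per day at risk are 0.1413/4.71 = 0.03 and 0.3062/10.21 = 0.03. The spurious gap disappears under the constant-risk assumption.

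**The case against.** The strongest reply is that the protocol nowhere confines adverse events to critical care. The instruction concerns daily recording. The data list it introduces contains items that cannot be completed there, the form stays open to hospital discharge, and the Ethics section also speaks of an in-hospital stage. A reader might infer from the schedule that ward events are certainly missed. The documents do not support that: the limitation is inferred, not stated. This part of the objection stands.

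It also stands that unequal stays are not established. The Introduction says that prolonged organ dysfunction in older patients lengthens hospital stay; it does not mention critical care stay. It also links MODS in older people to higher mortality, which would shorten observation. Readmissions to critical care are eligible, which would recover some events. No adverse-event comparison by MODS status is set out. Nothing says that any of the four centres has a separate Level 2 unit, so earlier stopping at some centres is hypothetical. A critical care window would also match that of the primary outcome.

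What does not stand is the step from room for ward capture to provision for it. Total stay and mortality need only a date and a status at discharge. Ward infection or stroke needs a deliberate search of the records, and no one is told to make it. If the sponsor does intend it, the sites cannot tell from this text.

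**Conclusion.** The point holds as a gap in the collection window with a conditional consequence. Outcome recording is tied to critical care in two places, and no provision is made for adverse events after step-down. If that is followed literally, and if critical care stays differ by age group, a simple comparison of proportions is distorted. The same applies by MODS status, should that comparison be made.

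A reader might go further and conclude that the age and MODS comparisons are biased. The documents do not show this. The risk ratios of 1.34 to 1.95 rest wholly on assumed stays and on an equal, constant daily hazard. Early death or readmission would change them, and equal stays would remove them.

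This is a worthwhile, inexpensive improvement to one secondary outcome. It does not touch the primary outcome or the sample size.

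**What to change.** 1. Reconcile sections 5 and 6 by stating one adverse-event window, running to hospital discharge.
2. Add adverse events (event, onset date, location) to the existing discharge step for completing the form, taken from routine records, and mark this in the Schedule of Assessment.
3. Compare groups by rate per observed day, or by cumulative incidence with death as a competing event. Extending the window alone is not enough, since hospital stay also varies. State how live discharge is handled. The per-day rate relies on a roughly constant daily risk, and recording location allows critical care and ward days to be separated. A common upper limit on follow-up is optional.
4. If collection is to stay within critical care, label the outcome as critical-care adverse events and report it per critical care day.

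Cost: one schedule entry, some wording on the form, and a modest record look-back at discharge. The work is not nil, since it covers up to 1346 patients and falls to local staff and the two funded research nurses, but the form is already open at that point and the in-hospital data come from routine care records.
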